## 15.29 Nursing Guidelines

- 15.291 Idelalisib can be taken with or without food and should be taken twice daily. Tablets must be swallowed whole. Doses should only be made up if less than 6 hours.
- 15.292 Gastrointestinal side effects are common, including diarrhea (including severe colitis), nausea, vomiting, etc. Treat symptomatically and monitor for effectiveness. Note that the diarrhea caused by this agent tends to respond poorly to antidiarrheal agents. Patients may need corticosteroids.
- 15.293 Serious and/or fatal hepatotoxicity can be seen. Monitor LFT's and instruct patients to report any abdominal pain, or jaundice to the study team.
- 15.294 Monitor CBC w/diff as neutropenia and thrombocytopenia is common. Instruct patients to report any signs or symptoms of infection and/or any unusual bruising or bleeding to the study team.
- 15.295 Rarely patients may experience pneumonitis. Instruct patients to report cough, shortness of breath, dyspnea, or chest pain to the study team.
- 15.296 Patients may experience pyrexia and/or chills. Rule out infection and treat symptomatically. Monitor for effectiveness.
- 15.297 Warn patients of potential fetal harm. Instruct women of child bearing potential to use appropriate and effective birth control while on agent.

## 15.3 Ibrutinib for Oral Administration (Imbruvica®)

- 15.31 **Background:** Ibrutinib is a potent and irreversible inhibitor of Bruton's tyrosine kinase (BTK), an integral component of the B-cell receptor (BCR) and cytokine receptor pathways. Constitutive activation of B-cell receptor signaling is important for survival of malignant B-cells; BTK inhibition results in decreased malignant B-cell proliferation and survival.
- 15.32 **Formulation:** Commercially available for oral administration as a capsule: 70 mg, 140mg (limited availability). Commercially available for oral administration as a tablet: 140 mg, 280 mg, 420 mg, and 560 mg..
- 15.33 **Preparation and storage:** Refer to package insert for complete dispensing instructions. Store capsules and tablets at room temperature between 20°C and 25°C (68°F and 77°F). Excursions are permitted between 15° and 30°C (59°F to 86°F). Keep in original container..
- 15.34 **Administration:** Refer to the treatment section for specific administration instructions. The manufacturer recommends Ibrutinib should be taken with water at the same time every day. Swallow capsules whole. Do not open, break, or chew the capsules. Do not cut, crush, or chew the tablets. Maintain adequate hydration during treatment. Hazardous agent; use appropriate precautions for handling and disposal.
- 15.35 **Pharmacokinetic information:**  
Distribution: ~10,000 L  
**Bioavailability:** Administration with food increased the maximum concentration by ~2 to 4-fold and the AUC 2-fold (compared with overnight fasting)

Protein binding: ~97%. Administration under fasting conditions resulted in exposure of ~60% compared to when administered either 30 minutes before or after a meal, or 2 hours after a high-fat meal.

**Metabolism:** Hepatic via CYP3A (major) and CYP2D6 (minor) to active metabolite PCI-45227

Half-life elimination: 4 to 6 hours

Time to peak: 1 to 2 hours

**Excretion:** Feces (80%; ~1% as unchanged drug); urine (<10%, as metabolites)

15.36 Potential Drug Interactions:

**Metabolism Effects:** Ibrutinib is primarily metabolized by cytochrome P450 enzyme 3A4/5. Avoid concomitant use of Ibrutinib with any of the following: CYP3A4 inducers (strong), CYP3A4 inhibitors (strong or moderate) and herbs that are CYP3A4 inducers or inhibitors. The levels of Ibrutinib may be increased by CYP3A4 inhibitors and decreased by CYP3A4 inducers (the active metabolite has inhibitory activity towards Bruton's tyrosine kinase that is approximately 15 times lower than that of Ibrutinib).

**Transport Effects:** Ibrutinib is a P-glycoprotein/ABCB1 inhibitor and may increase the serum concentrations of: afatinib, bosutinib, brentuximab, colchicine, active metabolites of dabigatran etexilate, doxorubicin, edoxaban, everolimus, ledipasvir, naloxegol, pazopanib, prucalopride, rifaximin, rivaroxaban, silodosin, topotecan and vincristine.

Ibrutinib may enhance the adverse/toxic effect of clozapine, leflunomide, natalizumab, pimecrolimus, tofacitinib, tacrolimus, and live vaccines. It may also enhance the adverse/toxic effect of anticoagulants and agents with antiplatelet properties. Dipyrone may enhance the adverse/toxic effect of Ibrutinib.

Grapefruit juice and Seville oranges moderately inhibit 3A4 and may increase Ibrutinib exposure.

15.37 **Known potential toxicities:** Consult the package insert for the most current and complete information.

Common known potential toxicities, >10%:

**Cardiovascular:** Peripheral edema, hypertension

**Central nervous system:** Fatigue, dizziness, headache, anxiety, chills

**Dermatologic:** Skin rash, skin infection, pruritis

**Endocrine & metabolic:** Increased uric acid, Hyperuricemia, hypoalbuminemia; hypokalemia, dehydration

**Gastrointestinal:** Diarrhea, nausea, constipation, abdominal pain, vomiting, decreased appetite, stomatitis, dyspepsia, gastroesophageal reflux disease, upper abdominal pain

**Genitourinary:** Urinary tract infection

**Hematologic & oncologic:** Decreased platelet count, bruise, neutropenia, decreased hemoglobin, hemorrhage, petechial, malignant neoplasm (secondary)

**Infection:** infection

**Neuromuscular & skeletal:** Musculoskeletal pain, arthralgia, muscle spasm, weakness, arthropathy

**Ophthalmic:** Dry eye syndrome, increased lacrimation, blurred vision, decreased visual acuity

**Respiratory:** Upper respiratory tract infection, dyspnea, sinusitis, cough, oropharyngeal pain, pneumonia, epistaxis, bronchitis

**Miscellaneous:** Fever, , falling

Less common known potential toxicities, 1% - 10%:

**Cardiovascular:** Atrial fibrillation, atrial flutter

**Infection:** Sepsis

Limited to important or life threatening:

**Renal:** Renal failure Increased serum creatinine

**Limited to important or life threatening:** Abnormal platelet aggregation, hepatic failure, hypersensitivity (includes anaphylactic shock, angioedema, urticaria), interstitial pulmonary disease, onychoclasia, pneumonia due to *Pneumocystis carinii*, pneumonitis, progressive multifocal leukoencephalopathy, reactivation of HBV, renal failure, Stevens-Johnson syndrome, tumor lysis syndrome

15.38 **Drug procurement:** Commercial supplies. Pharmacies or clinics shall obtain supplies from normal commercial supply chain or wholesaler.

15.39 Nursing Guidelines

15.391 There are numerous drug to drug interactions. Record all of patient's medications including OTC, and herbal use. Avoid concomitant use with agents as listed in section 15.16.

15.392 Patients should be instructed to avoid eating grapefruit (including juice) and Seville oranges while on Ibrutinib.

15.393 Peripheral edema is common. Instruct patients to report this to the study team.

15.394 Gastrointestinal side effects are common (diarrhea, nausea, constipation, abdominal pain, vomiting, etc). Treat symptomatically and monitor for effectiveness of intervention.

15.395 Monitor CBC w/diff. Instruct patients in energy conserving lifestyle (anemia) and to report any unusual bruising or bleeding and/or signs or symptoms of infection to study team.

15.396 Arthralgias, Myalgias, and muscle spasm can be seen. Treat symptomatically and monitor for effectiveness.

15.397 Monitor renal function/uric acid levels, especially in patients who may be experiencing dehydration.

15.398 Respiratory symptoms may include, cough, SOB, and URI. Instruct patients to report these symptoms to the study team.

15.399aRarely patients can experience secondary skin cancers. Instruct patients to report any new skin lesions to the study team.

15.399bRash can be seen. Instruct patient to report to study team.

15.399cCardiac arrhythmias have been seen with this agent including a-fib, atrial flutter and ventricular tachyarrhythmia's, some of which have led to

death. Instruct patients who experience any palpitations, lightheadedness, syncope, or SOB to seek medical care immediately. This is especially important in patients who have pre-existing cardiac issues.

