## 15.0 Drug Information

### 15.1 Pembrolizumab (MK-3475, SCH 900475, Keytruda®)

15.11 **Background:** Pembrolizumab is a potent humanized IgG4 monoclonal antibody with high specificity of binding to the PD-1 receptor, thus inhibiting its interaction with PD-L1 and PD-L2. Based on preclinical *in vitro* data, pembrolizumab has high affinity and potent receptor blocking activity for PD-1.

15.12 **Formulation:** Pembrolizumab is available as a liquid 25 mg/mL, 100 mg/vial.

15.13 **Preparation and storage:** Vials should be stored in the refrigerator at temperatures between 2-8°C.

Drug concentrate is further diluted with normal saline (or 5% dextrose in the concentration range of 1 to 10 mg/mL). The infusion solution in the IV bag should be immediately administered. Diluted pembrolizumab solutions may be stored at room temperature for a cumulative period of up to 6 hours. This includes room temperature storage of admixture solutions in the IV bags and the duration of infusion. The product can also be stored under refrigeration at 2°C to 8°C for no more than 96 hours from the time of dilution. If refrigerated, the diluted solution must be allowed to come to room temperature prior to administration. The solution must be discarded after 6 hours at room temperature or 96 hours under refrigeration

15.14 **Administration:** Pembrolizumab is administered by intravenous infusion over 30 minutes via a 0.22 micron in-line filter. The final infusion volume must be between 1 and 10 mg/mL. Maximum rate of infusion should not exceed 6.7 mL/minute through a peripheral or indwelling catheter. Flush the line with 0.9% NaCL following the completion of the infusion.

15.15 **Pharmacokinetic information:**

a) **Absorption** – Because pembrolizumab is administered intravenously, it is immediately and completely bioavailable. Steady -state concentrations of pembrolizumab are reached by 16 weeks of repeated dosing with a Q3W regimen and the systemic accumulation is 2.1-fold. The peak concentration, trough concentration, and area under the plasma concentration versus time curve at steady state of pembrolizumab increased dose proportionally in the dose range of 2 to 10 mg/kg Q3W.

b) **Distribution** – Pembrolizumab has a limited volume of distribution.

c) **Excretion** – CL is approximately 23% lower after achieving maximal change at steady state compared with the first dose. The terminal elimination half-life ( $t_{1/2}$ ) is estimated to be 22 days at steady state

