d) **Metabolism** - Pembrolizumab is catabolized through non-specific pathways; metabolism does not contribute to its CL.

15.16 **Potential Drug Interactions:** There are no known significant drug interactions.

15.17 **Very common known potential toxicities,  $\geq 10\%$**

Gastrointestinal disorders: diarrhea, nausea, abdominal pain

Skin and subcutaneous tissue disorders: rash, pruritis

General disorders and administration site conditions: fatigue

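### The ibrutinib nursing instruction in 15.391 points to the pembrolizumab interaction section (15.16), which lists no agents; the ibrutinib interaction text is in 15.36.

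*Combined protocol and SAP*

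**What the plan says.** Section 15.391 opens the ibrutinib nursing guidelines. It states "There are numerous drug to drug interactions", has staff record every medicine including over-the-counter and herbal products, and ends "Avoid concomitant use with agents as listed in section 15.16".

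The 15.1x numbers fall under "15.1 Pembrolizumab (MK-3475, SCH 900475, Keytruda". Section 15.16 is that drug's interaction entry and reads, in full, "There are no known significant drug interactions".

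Ibrutinib has its own monograph, headed "15.3 Ibrutinib for Oral Administration (Imbruvica", with its own interaction entry, "15.36 Potential Drug Interactions". That entry says "Avoid concomitant use of Ibrutinib with any of the following: CYP3A4 inducers (strong), CYP3A4 inhibitors (strong or moderate", and extends the list to herbs that induce or inhibit CYP3A4. It then lists drugs whose serum concentrations ibrutinib may raise through P-glycoprotein. On bleeding-related medicines it says "It may also enhance the adverse/toxic effect of anticoagulants and agents with antiplatelet properties".

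**The concern.** 15.391 is an operative instruction to the staff who take the medication history when ibrutinib is added to MK-3475 in Arms A and C. Section 7.3 recommends ibrutinib as the added agent for patients who have not used it before, so the instruction concerns a main path through the continuation phase.

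The reference does not lead to a missing section, which a reader would notice. It leads to a real section, for another drug, whose text is reassuring. A reader who follows it literally finds no agent to avoid. At stake is whether a relevant co-medication is recognised before or during combination treatment. Section 15.37 lists hemorrhage among ibrutinib toxicities above 10%, so the anticoagulant and antiplatelet warning is not a remote matter. Combination safety is also a secondary goal (2.24), tabulated under 16.328.

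**Working it through.** No formula applies; the check is to trace the reference and compare the texts.

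**1. Where the reference leads.**
- Source: 15.391, in the ibrutinib monograph (15.3).
- Target: 15.16, in the pembrolizumab monograph (15.1). Agents listed: none.
- The ibrutinib interaction entry: 15.36.

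Both interaction entries are present and legible, so redaction or text extraction does not explain the mismatch. The target also contradicts the opening of 15.391, which says the interactions are numerous.

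**2. What 15.36 contains.** It has two kinds of text.
- Agents to avoid, in three groups: strong CYP3A4 inducers; strong or moderate CYP3A4 inhibitors; herbs that induce or inhibit CYP3A4.
- Warnings without an instruction to avoid. These include 17 named entries whose concentrations may rise through P-glycoprotein (afatinib to vincristine, with edoxaban, rivaroxaban and the active metabolites of dabigatran among them), and anticoagulants and antiplatelet agents.

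**3. What the other controls cover.**
- 3.31 (continuation-phase exclusion): chronic strong CYP3A inhibitors or inducers, subject to investigator opinion; caution for moderate inhibitors.
- 8.2: caution with moderate cytochrome P450 inhibitors or inducers; package insert for dose adjustment when drugs interact.
- Appendix VII: home-medication review before ibrutinib or idelalisib starts, with lists of CYP3A agents, and package inserts for cytochrome P450 status.
- 15.392 and the patient diary (Appendix VI): grapefruit and Seville oranges.

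Of the 17 P-glycoprotein entries, one (everolimus) is in Appendix VII, and there as a CYP3A substrate; the other 17 − 1 = 16 are not in it. None of these controls states ibrutinib's P-glycoprotein warning or its anticoagulant and antiplatelet warning. Within the protocol, both appear only in 15.36.

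**4. A second mismatch seen on the way.** For moderate CYP3A4 inhibitors with ibrutinib, 15.36 says avoid, whereas 3.31 and 8.2 say caution. Correcting the reference in 15.391 does not settle this and would make it more visible.

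**5. Reach into the analysis.** The stopping rule in 16.52 counts only dose-limiting toxicities as defined in 16.4: specified hepatic abnormalities lasting over 4 weeks, grade 4 non-hematological toxicity lasting over 4 weeks (with stated exceptions), or any grade 5 event, at least possibly related to treatment. An interaction-related event enters that count only if it meets one of these. The tabulation in 16.328 is broader and would include it. The primary endpoint (16.11) is response to single-agent MK-3475, so events on the combination do not enter it.

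**The case against.** The strongest case on the other side is that this is a typographical slip with little consequence. The right text stands a few paragraphs earlier in the same monograph, and 15.391 says in its first sentence that interactions are numerous, so an attentive reader who reaches 15.16 would see that the number is wrong. Several controls do not depend on 15.391: those listed above, the continuation-phase eligibility checklist (6.9b), the provision in 7.3 to modify the ibrutinib dose for concomitant medications, the recording of concomitant medications (9.4), and the request in 15.395 that patients report unusual bruising or bleeding.

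Much of this stands. A reader might infer that the protocol's interaction check fails altogether, or that every Arm A or C patient who adds ibrutinib is put at risk. The documents do not support either. One look-up fails. The patients affected are those taking a relevant medicine that every other control also misses, and the documents give no number for them. Arm A closed to accrual in April 2016, and nothing says how many patients could still add ibrutinib.

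A reader might also infer that every drug named in 15.36 was meant to be avoided. That is not what 15.36 says: the P-glycoprotein, anticoagulant and antiplatelet texts describe what ibrutinib may do.

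What the objection does not remove is that an instruction to staff names the wrong drug's section, and that two of ibrutinib's warnings have no other place in the protocol.

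**Conclusion.** The cross-reference error is certain on the text. Its size is one failed look-up: 15.16 supplies no agents, while 15.36 supplies three groups to avoid and a separate set of warnings. Existing controls cover the CYP3A part and grapefruit to a fair extent. The P-glycoprotein and the anticoagulant and antiplatelet warnings are left to a reader who finds 15.36 unaided or consults the package insert.

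It is an internal inconsistency that bears on safety and should be corrected; it is not an absence of interaction guidance. It has no effect on the primary endpoint, the sample size or the decision rules. A reader might infer that it distorts the combination stopping rule in 16.52. The definition in 16.4 is narrow and the documents give no event frequency that would support that, so no such effect is shown.

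The conclusion assumes only that staff use 15.391 as written. How often they would correct the reference themselves is unknown.

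**What to change.** Reconcile the cross-reference in 15.391 with the ibrutinib interaction section, 15.36. Word it so that 15.36's own distinction survives between agents to avoid and agents that carry a warning; placing the whole of 15.36 under an instruction to avoid would create prohibitions that 15.36 does not contain.

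Do not add Appendix VII to 15.391 as an avoid list. It includes moderate inducers, which 15.36 does not say to avoid, moderate inhibitors, for which 3.31 and 8.2 say caution, and CYP3A substrates, which are an idelalisib criterion in 3.32. Adding it would choose a clinical rule rather than correct a reference.

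In the same amendment, the sponsor should reconcile 15.36 with 3.31 and 8.2 on moderate CYP3A4 inhibitors. This review takes no position on which is right.

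The cost of the first change is one cross-reference and a few words, with no new procedure, visit or analysis. The second needs a decision by the sponsor and matching text in the three sections.

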## 16.0 Statistical Considerations and Methodology

16.1 Overview: This Phase II study will utilize a one-stage binomial design in each arm independently (Arms A, B, and C) to assess the overall response rate associated with single-agent MK-3475 in patients with relapsed and progressive CLL/SLL, including CLL patients with Richter's transformation (RS) or Hodgkin's transformation (Arm A and Arm C) and other types of relapsed and progressive low grade B cell NHL including FL, WM and marginal zone lymphoma (Arm B).

16.11 Endpoint: The primary endpoint of this trial is the proportion of patients who achieve a confirmed response to single-agent MK-3475. A confirmed response is defined to be a PR, nPR, CCR, CRi or CR (Arms A and B) or CMR, PMR, PR, or CR (Arm C) noted as the objective status at any time while on single-agent MK-3475. All patients meeting the eligibility criteria who have signed a consent form and have begun treatment will be evaluable for response, with the exception of patients determined to be a major violation.

16.12 Sample Size: This study is expected to require a maximum of 23 evaluable patients each in Arm A and Arm B. We anticipate accruing 1 additional patient in each arm to account for ineligibility, cancellation, major treatment violation, or other reasons. Therefore, this study is expected to accrue between 46 - 48 patients in these two arms.  
As of MCCC Addendum 3, due to promising response observed in CLL patients with Richter's transformation, an additional arm (Arm C) with 17 evaluable patients is added to the trial. We anticipate accruing 3 additional patients to account for ineligibility, cancellation, major treatment violation, or other reasons for a total of 20 patients on Arm C. These patients will be accrued to allow better evaluation of response and toxicity of single agent MK 3475 in patients with Richter's transformation. This study is now expected to accrue a maximum of 68 patients.

16.13 Accrual Rate and Study Duration: The anticipated accrual rate is approximately 2-4 patients per month. Therefore, the accrual period for this phase II study is expected to be approximately 2-3.0 years. The final analysis can begin as soon as the last patient has been observed for 6 months, or at approximately 3.0-3.5 years.  
MCCC Addendum 3: In approximately 20 months, the study has accrued 41 patients. Based on current accrual rates, the total accrual period is now expected to be approximately 3.0 years. The final analysis can begin as soon as the last patient has been observed for 6 months, or approximately 3.5 years from trial opening.

16.2 Statistical Design:

16.21 Decision Rule for Arms A and B (to be evaluated in each arm independently): MK-3475 monotherapy induces an ORR of 39% in patients with ipilimumab-naïve melanoma by central independent RECIST review. The potential activity of this agent in relapsed CLL or low grade NHL has not been tested. Previous approved monoclonal antibodies, alemtuzumab or rituximab, have achieved ~20-30% ORR in CLL. We expect that CLL patients who develop resistance to novel CLL therapies will enroll into this clinical study. It is completely unknown how CLL patients will respond to any types of CLL therapy after they developed

Ibrutinib resistance. Therefore, it is logical to hypothesize that 30% ORR will be worthy of further testing in relapsed CLL and low grade NHL patients.

The largest success proportion where the proposed treatment strategy would be considered ineffective in this population is 10%. The smallest success proportion that would warrant subsequent studies with the proposed treatment strategy in this patient population is 30%. The following one-stage binomial design uses 23 evaluable patients to test the null hypothesis that the true success proportion in a given patient population is at most 10%.

16.211 Final Decision Rule: Enter 23 evaluable patients into the study. If 4 or fewer successes are observed in the first 23 evaluable patients, we will consider this regimen ineffective in this patient population. If 5 or more successes are observed in the first 23 evaluable patients, we may recommend further testing of this regimen in subsequent studies in this population.

16.212 Over Accrual: If more than the target number of patients are accrued, the additional patients will not be used to evaluate the stopping rule or used in any decision making process. Analyses involving over accrued patients are discussed in Section 16.34.

16.22 Assuming that the number of responses is binomially distributed, with a significance level of 7%, the probability of declaring that the regimen warrants further studies (i.e., statistical power) under various response proportions can be tabulated as a function of the true response proportion as shown in the table below.

If the true success proportion is...	0.10	0.15	0.20	0.25	0.30
Then the probability of declaring that the regimen is promising and warrants further study is...	0.07	0.26	0.50	0.72	0.86

16.23 Decision Rule for Arm C:

In the 9 Richter's transformation patients accrued to Arm A of this study, 4 patients were classified as a PET-CT or CT response by the Lugano 2014 response criteria. Due to the promising efficacy in selected patients with Richter's transformation, Arm C is being added to further test efficacy of this agent in this patient population. A confirmed response rate of 40% would be considered promising and would be of significant clinical interest. However, a response rate of 15% would be considered ineffective.

The largest success proportion where the proposed treatment strategy would be considered ineffective in this population is 15%. The smallest success proportion that would warrant subsequent studies with the proposed treatment strategy in this patient population is 40%. The following one-stage binomial design uses 17 evaluable patients to test the null hypothesis that the true success proportion in a given patient population is at most 15%.

16.231 Final Decision Rule: Enter 17 evaluable patients into the study. If 4 or fewer successes are observed in the first 17 evaluable patients, we will consider this regimen ineffective in this patient population. If 5 or more

successes are observed in the first 17 evaluable patients, we may recommend further testing of this regimen in subsequent studies in this population.

16.232 Over Accrual: If more than the target number of patients are accrued, the additional patients will not be used to evaluate the stopping rule or used in any decision making process. Analyses involving over accrued patients are discussed in Section 16.34.

16.24 Assuming that the number of responses is binomially distributed, with a significance level of 10%, the probability of declaring that the regimen warrants further studies (i.e., statistical power) under various response proportions can be tabulated as a function of the true response proportion as shown in the table below.

If the true success proportion is...	0.15	0.20	0.25	0.30	0.35	0.40
Then the probability of declaring that the regimen is promising and warrants further study is...	0.10	0.24	0.43	0.61	0.77	0.87

16.25 Other considerations: Adverse events, quality/duration of response, and patterns of treatment failure observed in this study, as well as scientific discoveries or changes in standard care will be taken into account in any decision to terminate the study

